#### **RFID** system validation

We will validate the RFID technology against a human timekeeper control for the time to bundle of care outcome by investigating bias and accuracy using a Bland

Altman analysis. The RFID technology will be considered as interchangeable with a human timekeeper if the 95% limits of agreement fall within +/-5 min. We chose this cut off as delays in bundle of care delivery below this threshold is unlikely to be of clinical significance. We will use the first 100 pairs of RFID and human measurements to calculate a mean difference and standard deviation of difference between the two measurements. Using these two values and a clinically acceptable limit of 5 min, with an alpha of 0.05 and beta of 0.2, we will calculate the sample size required for the Bland Altmann analysis by methods previously described [23]. If the 95% limits of agreement fall outside of 5 min, the same Bland Altman analysis will be done for the patient arrival time and time of bundle of care delivery; these comprise of the start and end time components of the time to bundle of care outcome. These secondary analyses serve to ascertain which of the two components contains the larger discrepancy between RFID and human measurement. Should these secondary analyses be necessary, implementation issues in the RFID technology will be brainstormed in focus groups with the technology team and addressed on the ground, and we will repeat the same validation process as described. After successful logistical improvements and validation of the RFID technology to within 5 min of a human timekeeper, we will utilize the RFID technology for data collection with a human timekeeper as backup as needed.

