### **Time Outcomes**

Timing tracking will be automated using customised RFID. RFID uses radio-frequency electromagnetic fields to identify the location of patients carrying special tags, with the help of readers located in key locations around the hospital, including the registration area, triage examination rooms, and treatment rooms. We intend to use Low Energy Bluetooth (BLE) tags that have a diameter of approximately 3cm and weigh <20g (see Figure 1). These tags will be inserted into a custom, washable arm, wrist or leg band. The tag could also be retained by the caregiver if the child was not willing to have the tag attached to them. When in close vicinity to a reader (for example, in the same room), the tag (location beacon) sends a message to a strategically located receiver to track the time at which the patient was in that precise location. Initially, manual tracking will also be conducted by designated study staff who will be situated in the same key locations as the RFID readers in order to validate the RFID system and ensure optimal performance.

Figure 1: Picture of RFID patient tracking tag

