#### Time outcomes

Timing tracking will be automated using customised RFID (see RFID system section for details).

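### RFID is accepted on limits of agreement among paired readings alone, so missed tag reads affect neither the accept decision nor the repeat-validation trigger

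*Combined protocol and SAP*

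**What the plan says.** The acceptance rule stands only in the published protocol, under *RFID system validation*: "The RFID technology will be considered as interchangeable with a human timekeeper if the 95% limits of agreement fall within +/-5 min". The quantity compared is time to bundle of care, and the unit is the pair: "We will use the first 100 pairs of RFID and human measurements to calculate a mean difference and standard deviation of difference". The final number of pairs is then derived from those values: "with an alpha of 0.05 and beta of 0.2, we will calculate the sample size required for the Bland Altmann analysis".

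Troubleshooting and repeat validation depend on the same limits: "If the 95% limits of agreement fall outside of 5 min, the same Bland Altman analysis will be done for the patient arrival time", and likewise for the bundle delivery time. Once RFID passes, "we will utilize the RFID technology for data collection with a human timekeeper as backup as needed". When the backup is needed is not defined.

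Protocol v5.0, section 15 (*Time Outcomes*), describes parallel running without an acceptance criterion: "Initially, manual tracking will also be conducted by designated study staff who will be situated in the same key locations as the RFID readers". Objective 2 of the published protocol names accuracy as what the comparison evaluates. None of these sections gives a capture rate, a limit on missed reads, or a rule for children with a human time and no RFID time.

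**The concern.** A Bland-Altman difference exists only when both methods return a value. A child whose arrival and treatment were timed by the human, but whose tag was not read at one of those points, has no difference and leaves the validation set without trace. The component analyses for arrival and bundle delivery also need pairs, so they cannot show the loss either. The rule therefore measures agreement given a successful read, while the conclusion it licenses is that RFID can replace the timekeeper.

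Missed reads are plausible. The tag must be close to a reader, and the caregiver may keep it instead of the child.

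Two things are at stake. The direct one is Objective 2, because a system with poor capture could be declared interchangeable. The indirect one is the endpoint of bundle of care within one hour, which uses these times. From RFID alone, a child who was never given a bundle and a child whose tag was not read can look the same. The outcomes analysis does not say how a blank time is handled.

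**Working it through.** **Inputs.** From the published protocol: the ±5 min criterion and 100 initial pairs (*RFID system validation*); a baseline of 27% and a 20% relative increase, so 0.27 × 1.2 = 32.4%, a gain of 5.4 points (*Sample size*); and a primary analysis by difference-in-differences on bundle within one hour (*Outcomes analysis*). The documents give no missed-read rate, so *m* is an assumption shown over a range. The RFID section states no derived figure to reproduce: ±5 min and 100 pairs are chosen values, and the Bland-Altman sample size is deferred.

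**1. What the rule responds to.** Largest SD of differences that passes = (5 − |bias|)/1.96.
- Bias 0: 5/1.96 = 2.55 min
- Bias 1 min: 4/1.96 = 2.04 min
- Bias 2 min: 3/1.96 = 1.53 min

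The share of reads lost does not enter.

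**2. Simulation of the rule on 100 pairs.** Assumed: RFID minus human difference Normal with mean 0.5 and SD 2 min; lognormal time to bundle with 32.4% within 60 min; timing error in the readings obtained unrelated to whether other reads fail. Expected limits are 0.5 ± 1.96 × 2, or −3.4 to +4.4 min. With 0, 10, 20, 30 and 50% of reads lost, either at random or twice as often in children treated within 60 min, the limits stayed there and the chance of passing was 95% to 97%. Children needed for 100 pairs = 100/(1 − *m*): 111, 125, 143 and 200 at 10, 20, 30 and 50% lost. The rule reports none of these.

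**3. Endpoint, if a blank time is coded as a failure and loss is equal in both groups.** Assume misses unrelated to speed, human-timed baseline, RFID-timed later period, and a control hospital staying at 27%. The baselines cancel:

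Difference-in-differences = [0.324(1 − *m*) − 0.27] − [0.27(1 − *m*) − 0.27] = 0.054(1 − *m*).

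| *m* | Intervention | Control | Difference-in-differences |
|---|---|---|---|
| 0 | 32.4% | 27.0% | 5.4 points |
| 5% | 30.8% | 25.7% | 5.1 |
| 10% | 29.2% | 24.3% | 4.9 |
| 20% | 25.9% | 21.6% | 4.3 |

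The ratio of odds ratios moves from 1.30 (*m* = 0) to 1.28 (10%) and 1.27 (20%).

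**4. Endpoint, if loss falls only on the intervention hospitals' later period.** The apparent gain is 0.324(1 − *m*) − 0.27: 3.8 points at 5%, 2.2 at 10%, 0 at 16.7% and −1.1 at 20%.

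**5. Endpoint, if blank times are dropped.** Random loss leaves the proportion at about 32%. If children treated within 60 min are missed twice as often, the observed proportion is 0.324(1 − 2*b*)/(1 − *m*) with *b* = *m*/1.324: 30.6% at 10% lost, 28.3% at 20% and 25.3% at 30%. The simulation, which includes the 0.5 min bias, gave about 30, 28 and 25%. These are one-group levels, not treatment effects.

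**The case against.** The strongest reply is that the gap need not reach the primary endpoint, and most of that reply stands.

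- **Manual times exist.** In v5.0, section 14 has a timekeeper record arrival times in a notebook. Appendix A has a separate arrival-time field and a Clinical Timekeeper form with start times for antibiotics, fluids and oxygen. The tag reports only location, so some other record is needed to know what was given. The documents do not say who completes that form after RFID is adopted, but they give no ground for assuming that the times vanish.
- **A backup and checks exist.** A human timekeeper is kept as backup. Both data monitoring sections call for regular completeness reports and for inspection of the timed outcome data. These could recover or reveal losses, but they carry no threshold and do not enter the acceptance decision.
- **The coding is not stated.** No section scores a missing time as untreated within 60 minutes.
- **The rule is absent from v5.0.** That is so, but v5.0 gives no other acceptance criterion, so it does not close the gap.

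A reader might infer from step 4 that about 17% missed reads would wipe out the planned effect. The documents do not support this. Those are one-group figures, whereas the published primary analysis has a control group, and equal loss there mostly cancels. Erasure or reversal needs read rates that differ between hospitals, or RFID timing at intervention sites only, and neither is stated. Section 17 of v5.0 also lists a historical comparison. The one-group arithmetic would apply to it only if the timing source changed between phases and blanks were coded as failures, which the documents do not state either.

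What the reply does not answer is the acceptance rule itself, which ignores capture.

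**Conclusion.** The point holds as a defect of the RFID acceptance rule. Under the stated assumptions, a system losing half its reads passes about as often as one losing none, so Objective 2 can receive a wrong answer. That exclusion follows from the method; the documents do not spell it out.

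The effect on the primary endpoint is possible but not shown, and it depends on a coding rule that the plan leaves open. With blanks coded as failures and equal loss in both groups, the attenuation is modest: 5.4 points becomes about 4.9 at 10% missed and 4.3 at 20%. With randomly missing times dropped, there is almost no bias. Larger damage requires unequal capture between hospitals, RFID timing at intervention sites only, or loss related to speed of treatment. Nothing in the plan says that any of these will occur, and the acceptance rule would not reveal them.

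**What to change.** **At validation.** While both systems run, take as denominator every child with a human-timed arrival and bundle start. Report the share with both RFID times, with a confidence interval, by hospital and phase. Make a pre-set minimum capture rate a second acceptance condition and a repeat-validation trigger, alongside ±5 min.

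The sponsor should choose and justify that minimum together with the number of children, because the documents give no basis for a particular value. As an illustration, requiring a one-sided 95% lower bound of at least 95% with 200 children allows at most 4 missed (196/200 gives 95.5%; 195/200 gives 94.8%). That would fail a system with true capture of 97% about 72% of the time, and one with 98% about 37% of the time.

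**After adoption.** State that a missing RFID time is not scored as untreated within 60 minutes. Use the manually recorded arrival time and the Clinical Timekeeper treatment time where they exist; otherwise treat the time as missing. Define when the human backup is used, and report missed reads by hospital and phase.

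**Cost.** The validation part is a tally on data already being collected, plus analysis-plan wording. The downside is that RFID may be accepted later, so human timekeepers may run longer.

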### **Involved in Phase I only:**

3. Control Site: Kiambu County Referral Hospital in Nairobi, Kenya

A typical outpatient department (OPD) in the Kenyan study hospitals serves approximately 20,000 children per year and is staffed by one or two nurses who conduct triage and administer treatment, two or three clinicians who review patients and issue prescriptions, and one additional nurse who administers treatment and provides counselling to caregivers of children. The hospitals admit approximately 2,000 pediatric patients per year.

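### The RFID acceptance rule carries no confidence bounds, so the alpha used to plan the number of pairs does not reach the decision; separately, the check cannot cover children with no bundle time

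*Combined protocol and SAP*

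**What the plan says.** The acceptance rule is in the published protocol, under RFID system validation. The variable compared is time to bundle of care, RFID against a human timekeeper. The planning step reads "We will use the first 100 pairs of RFID and human measurements to calculate a mean difference and standard deviation of difference", and then, "with an alpha of 0.05 and beta of 0.2, we will calculate the sample size required for the Bland Altmann analysis by methods previously described". The decision step says that the technology "will be considered as interchangeable with a human timekeeper if the 95% limits of agreement fall within +/-5 min". No confidence interval for the limits is mentioned.

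If the limits fall outside the margin, arrival time and bundle time are examined separately, problems are dealt with on site, and "we will repeat the same validation process as described". No maximum number of attempts, error control or rule on which pairs may be used is given. After a pass, RFID supplies the times and a human timekeeper is kept as backup.

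The tag works "to track the time at which the patient was in that precise location" (protocol version 5.0, Time Outcomes; the RFID system section of the published protocol says the same). The primary analysis in the published protocol (Outcomes analysis) is a logistic model for receipt of the bundle within one hour.

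Protocol version 5.0, which is later than the published protocol, says that manual tracking will run at first to validate RFID, but gives no acceptance criterion.

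**The concern.** This check decides which instrument times the primary outcome. Planning with alpha 0.05 and beta 0.2 implies a test with controlled error. A rule that asks only whether two estimates fall inside a margin has no such control: when a true limit is at the margin, its estimate falls inside roughly half the time, whatever the number of pairs. The plan would then size the validation for one kind of decision and take another. An uncapped repeat adds further chances to pass.

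The second issue is coverage, not alpha. A pair for time to bundle needs a bundle time from both sources. A child who never received an antibiotic, intravenous fluid or oxygen has none from the timekeeper and so cannot enter the comparison. That child still counts in the binary primary outcome, as not treated within the hour. Agreement on times among treated children does not show that the two sources agree on who was treated in time.

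**Working it through.** **Inputs.** From the published protocol: margin ±5 minutes; limits = mean difference ± 1.96 × SD; alpha 0.05 and beta 0.2 for planning; first 100 pairs. The documents give no mean difference, SD or final number of pairs, so bias and SD below are assumptions, and differences are taken as normal. There is no planned number of pairs to reproduce.

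**Rule as written.** With mean d and standard deviation s from n pairs, accept if d + 1.96s < 5 and d − 1.96s > −5. The acceptance probability follows by integrating over the normal distribution of d and the chi-square distribution of s.

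True limit exactly at the margin, SD = (5 − bias)/1.96:

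| Bias (min) | SD (min) | n = 100 | n = 400 | n = 1000 |
|---|---|---|---|---|
| 0 (both limits at 5) | 5/1.96 = 2.551 | 0.316 | 0.308 | 0.306 |
| 1 (one limit at 5) | 4/1.96 = 2.041 | 0.514 | 0.507 | 0.504 |
| 2 (one limit at 5) | 3/1.96 = 1.531 | 0.514 | 0.507 | 0.504 |

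Simulation with 100,000 runs at n = 100 gave 0.318 (bias 0) and 0.515 (bias 1).

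**Beyond the margin.** True outer limit U, SD = (U − bias)/1.96:

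| U (min) | Bias 0, n = 100 | Bias 1, n = 100 | Bias 0, n = 400 | Bias 1, n = 400 |
|---|---|---|---|---|
| 5.25 | 0.132 | 0.261 | 0.038 | 0.091 |
| 5.5 | 0.044 | 0.106 | 0.002 | 0.005 |
| 6 | 0.003 | 0.011 | <0.001 | <0.001 |

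**Repeats.** If the system is unchanged and attempts are independent, the chance of at least one pass in three is 1 − (1 − p)³. At the margin with n = 100 this is 1 − 0.684³ = 0.68 and 1 − 0.486³ = 0.89. Even a true 0.05 rule would give 1 − 0.95³ = 0.143.

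**With confidence bounds.** The approximate standard error of a limit is s × √(1/n + 1.96²/(2(n − 1))). At n = 100 the root is 0.1715. Multiplied by the t quantile, it widens each limit by 0.340s, so 1.96 becomes 2.300. False acceptance at the margin is then 0.007 (both limits there) or 0.039 (one limit there).

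**Pairs needed for 80% power under that rule, zero bias.** SD 2.0 (limits ±3.92): 108. SD 2.25 (limits ±4.41): 438.

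**Children with no bundle.** The planning rate is 27% within one hour, so 73% are not treated within the hour. That is not the share outside the check: children treated later have bundle times and form pairs. Only the never-treated are outside it, and the documents give no rate for them.

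**The case against.** Alpha 0.05 is stated for the sample-size calculation and not as the error rate of the acceptance rule, so a reader who concluded that the rule breaks its own stated alpha would go too far. The cited sample-size method may itself use confidence bounds. This stands; what remains is that the decision as written does not mention them.

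A reader might also infer that a poor device would often be accepted. The second table does not support that: the excess is large only close to 5 minutes and shrinks quickly beyond it.

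The three-attempt figures could be read as the plan's expected error. They are not. Each repeat follows an attempt to correct the system, so they apply only if the correction changed nothing. Repeating the process may also mean starting with a new first 100 pairs, but the text does not say so.

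Finally, a reader might infer that a visit to the treatment room will be scored as a bundle, particularly because typical staffing at the Kenyan hospitals includes "one additional nurse who administers treatment and provides counselling to caregivers of children". No section says this. The staffing description does not place counselling in the treatment room, and the Clinical Timekeeper form in Appendix A of version 5.0 records the start of antibiotics, fluids, oxygen and antimalarials separately. The open point is narrower: the documents do not state how RFID times and form entries are combined, and the validation does not test agreement in untreated children.

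**Conclusion.** The concern holds in a limited form. The acceptance rule as written uses estimated limits of agreement alone, and the planning alpha is not carried into it. At the margin it accepts about 32% to 51% of the time with 100 pairs, and no larger number brings this near 5%. The practical excess concerns devices just outside the margin. These figures rest on normal differences and on assumed bias and SD. Repeats lack stated error control and a fresh-pair rule; how much this matters depends on whether the repairs work.

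The coverage gap is a separate finding. It is inferred from what a pair requires and from the documents' silence on untreated children, and its size cannot be derived from them. Neither part shows that the primary result would be biased. Both leave the choice of timing instrument less well supported than the plan suggests.

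**What to change.** 1. Accept RFID only if the 95% confidence intervals of both limits of agreement lie inside ±5 minutes, and size the validation for that rule. State the interval method and whether the first 100 pairs count towards the decision.
2. Base each repeat only on new pairs collected after the last system change, and report the number of attempts. A fixed cap is not essential for a device that has been repaired.
3. As a separate criterion, report agreement between RFID and timekeeper on bundle within 60 minutes (yes/no) in all tagged children, treated or not, with its confidence interval.
4. Take whether a component was given, and which one, from the existing Clinical Timekeeper fields; use RFID only for location times.
5. Carry the rule into protocol version 5.0, which has no acceptance criterion.

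The cost is mostly wording. More paired readings may be needed if the device is close to the margin: about 440 at an assumed SD of 2.25 minutes and zero bias, against about 110 at SD 2.0. The timekeeper form must stay in use to record treatment receipt.

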#### **Outcomes** analysis

We will be conducting our primary analysis using a difference in differences method. For our primary analysis, a logistic regression model for receipt of bundle of care within 1 h will be fit including: 1) phase of study (pre vs. post PRST) and 2) group (intervention versus control) as independent dummy variables and 3) their interaction. The interaction term corresponds to the difference in log-odds between groups in baseline vs intervention and it's exponent as the ratio of odds ratios. We will summarise this difference by estimating the marginal effect (risk difference) of phase in both the control and intervention groups. The difference of these marginal effects is the so-called 'difference in difference' for a binary outcome [24]. Confidence intervals will be based on the delta-method, or bootstrapping, where appropriate. A similar approach will be used for binary secondary outcomes (mortality, readmission), or quantile regression for median time to bundle of care, a non-parametric outcome.

Subgroup analyses specified a priori include Ugandan vs. Kenyan intervention site, young infant (under 2 months old) vs. children under 5 vs. older children, and presentation during day-shift hours versus night-shift hours (if applicable). We will also perform subgroup analyses on each triage category (emergency, priority, queue); patients from the pre-intervention phase will be retroactively categorized into these subgroups for this analysis. These subgroup analyses will be conducted with the inclusion of a three-way interaction between said variable, phase, and group. Statistical significance will be based on a likelihood ratio test comparing models with and without this term. This three-way interaction term would represent potential interactions between different subgroups and our difference in odds ratio obtained in our primary analysis, and results will again be presented on the risk difference scale based on marginal effects. This method of subgroup analysis sometimes termed a difference in difference in differences method.

Although none are expected, if there are any time varying confounders identified during the study that differ between intervention and control (health system or policy changes, natural events, changes in patient populations etc.) they will be included in above models as sensitivity analyses.

As we are continually collecting data regarding predictors for admission alongside the clinical team, there is the possibility that our research activities may interact with the efficiency of delivering the sepsis bundle of care. Although the possibility of such interaction is minimized by our use of dedicated research personnel who would not approach patients who are actively receiving clinical care, any such interactions could potentially limit the external validity of our study to non-researchcontrolled settings. Therefore, to assess this potential interaction, we will pause the collection of predictor data 1 month before and after implementation of the PRST program. This pause will also occur in the control group in order to replicate any bias caused by changes in our primary outcome attributable to the pause rather than the PRST program. To investigate the potential for this bias, we will treat the collection or non-collection of predictors as a dummy variable for subgroup analysis using the difference in difference in differences method described above.

All analyses will be conducted using R statistical software [25], and an alpha level of 0.05 will be considered statistically significant for all outcome analyses.

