### Changes due to COVID-19

The global COVID-19 has introduced many challenges to the successful completion of this project. We have been unable to initiate Phase I of the project in Nairobi, Kenya due to restrictions implemented to reduce the risk of spread of COVID-19. We have made good progress in recruitment in Jinja, Uganda. I consultation with our investigators, implementation partners and funders we have decided to add an additional site at Gulu Regional Hospital in Uganda. Gulu Regional Referral Hospital will serve as a control site while the intervention phase (Phase III) takes place at Jinja Regional Referral Hospital. Once the intervention period has been completed in Jinja, the intervention will be introduced at Gulu Regional Referral Hospital.

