#### **Outcomes Analysis**

We will compare the proportion of children at the two intervention sites receiving a completed bundle within 60 minutes to the historical and the contemporaneous control group (Marascuillo procedure). The median time to an appropriate bundle of care will be compared using a Mann–Whitney U test. The triage prioritization between the phases and the proportion of children who received and appropriate bundle of care within each triage categorization will be compared with Fisher's exact tests. Segmented regression analysis of the interrupted time series of the pre- and post- intervention periods will be used to assess immediate effects and effects over time, controlling for prior trends that may continue without our intervention. Quantile regression will be used to estimate the median differences. We will compare the estimated times at end of the intervention period with the expected counterfactual value, had the pre-intervention trend continued as if the intervention never occurred. We will compare the time to event (treatment bundle) using the Kaplan-Meier estimator with censure at 180 minutes. Secondary outcomes will be compared using generalized estimating equations.

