The main objective of the PRST is to enable frontline health workers to recognize the most urgent children more rapidly and allocate necessary resources more efficiently. We designed the PRST specifically for use in low-resource settings. The mobile application, integrated pulse oximetry sensors, and dashboard are easily accessible, affordable, robust to internet and power interruptions (system includes a secure local network that does not require an active internet connection) and do not rely on sophisticated expertise to operate.

Performance of the PRST may vary depending on geographical location, season, and with different disease prevalence and severity. Standardized measurements will be collected at sites in both Kenya and Uganda in order to explore these differences and optimize performance of the PRST at each site. External validation will be necessary to determine generalizability in other LMICs.

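### The published primary model pools two intervention hospitals under one group dummy with no site term, so a change in site mix between phases can bias the effect

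*Combined protocol and SAP*

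**What the plan says.** **Published protocol (June 2020), Outcomes analysis.** The primary logistic model for receipt of the bundle within 1 h has three terms: phase (before or after the tool), "2) group (intervention versus control) as independent dummy variables", and their interaction. The result is summarised as a difference of marginal risk differences. The Study sites list gives two experimental hospitals, Jinja (Uganda) and Mbagathi (Kenya), and one control, Kiambu (Kenya).

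Site enters only as a subgroup: "Subgroup analyses specified a priori include Ugandan vs. Kenyan intervention site". Time-varying confounders that differ between intervention and control are covered if they are identified during the study, and then "they will be included in above models as sensitivity analyses".

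**Protocol v5.0 (October 2020), section 17, Outcomes Analysis.** This section has no difference-in-differences model and no group dummy. It states "We will compare the proportion of children at the two intervention sites receiving a completed bundle within 60 minutes to the historical" and contemporaneous control groups, and it names no site adjustment.

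**Protocol v5.0, section 8, Changes due to COVID-19.** Phase I had not started in Nairobi. Gulu is added as a control during Jinja's Phase III. Then: "Once the intervention period has been completed in Jinja, the intervention will be introduced at Gulu Regional Referral Hospital".

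**Enrolment.** Both documents target 4,000 children per site with at least 1,000 in Phase I. Section 13 of v5.0 adds 250 per experimental site in Phase I. Neither document sets numbers by site and phase.

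**The concern.** A single dummy for two hospitals treats them as one population whose make-up is the same before and after. If the make-up changes, the pooled intervention rate moves even when nothing changes inside either hospital. The lone control hospital cannot mirror that movement, so it passes straight into the interaction term, which is the primary effect. It can create an apparent benefit or hide a real one.

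Two conditions are needed, and both are plausible here without being established.

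- **Unequal baseline rates.** The published Model development section notes high malaria prevalence in Jinja. The bundle counts antibiotics, intravenous fluids or oxygen, and the v5.0 data dictionary times antimalarials separately. The published Discussion expects site differences: "Performance of the PRST may vary depending on geographical location, season, and with different disease prevalence and severity". That sentence concerns the tool's performance, so unequal timeliness of care is an inference from it.
- **A shift in shares.** Phase lengths are given as ranges, there is no site-by-phase quota, and Kenya was delayed while Jinja was recruiting.

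**Working it through.** **Planned effect.** The published Sample size section assumes 27% at baseline and a 20% relative increase: 0.27 × 1.20 = 0.324, a difference of 5.4 points.

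**The plan's 750 per group.** The standard two-sided two-proportion formula, with mean rate 0.297, gives

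n = [1.96·√(2·0.297·0.703) + 0.842·√(0.27·0.73 + 0.324·0.676)]² / 0.054² ≈ 1,123.

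The stated 750 is not reproduced. The present point does not depend on it; 750 serves below only as an illustrative cell size.

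**Bias formula.** Let the intervention hospitals have baseline rates pA and pB, with hospital A's share w0 before and w1 after. Assume no true effect and no change at the control.

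- Pooled rate before: w0·pA + (1 − w0)·pB
- Pooled rate after: w1·pA + (1 − w1)·pB
- Spurious difference in differences: (w1 − w0)·(pA − pB)

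**Numbers put in** (all rates and shares are assumptions):

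| Rates A, B | Share of A | Before | After | Bias |
|---|---|---|---|---|
| 30%, 20% | 50% to 70% | 25.0% | 0.7·30 + 0.3·20 = 27.0% | +2.0 points |
| 35%, 20% | 50% to 80% | 27.5% | 0.8·35 + 0.2·20 = 32.0% | +4.5 points |

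Over gaps of 5 to 30 points and shifts of 10 to 50 points, the bias runs from 0.5 (5 × 10%) to 15 points (30 × 50%).

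**Effect on the test.** Take 750 children in each of the four cells, a mean baseline rate of 27%, a 20-point shift and no true effect. The standard error is √[Σ p(1 − p)/750] over the four cells, about 3.2 points.

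| Gap | Spurious difference | Ratio of odds ratios | False-positive rate (nominal 5%) |
|---|---|---|---|
| 10 | 2.0 | 1.10 | 9% |
| 20 | 4.0 | 1.22 | 23% |
| 30 | 6.0 | 1.33 | 45% |

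With site effects and a treated indicator in place of the group dummy, the ratio of odds ratios is 1.00 in every scenario. Each hospital is then compared with itself, so shares drop out.

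**Do the enrolment rules exclude such shifts?** Read 4,000 as the total over both phases. Suppose one hospital enrols 1,000 then 3,000 and the other 2,000 then 2,000. Both meet the target and the Phase I minimum. The first hospital's share goes from 1,000/3,000 = 33.3% to 3,000/5,000 = 60.0%, a shift of 26.7 points. The split is hypothetical, but the rules allow it.

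**Gulu after its switch.** If its later data were coded as control and made up a fraction f of the control group's post-phase children, a true 5.4 points would appear as 5.4·(1 − f): 4.9, 4.05 and 2.7 points for f = 10%, 25% and 50%.

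**The case against.** The case on the other side is substantial.

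- **No site-specific rates.** The documents give one baseline figure, 27%. A reader might infer that the hospitals are known to differ in bundle rates; they are not. The figures above are illustrations. This stands.
- **The design leans towards balance.** Both experimental hospitals share a schedule and a target, the extra 250 applies to each, and recruitment is paced by nurse time rather than hospital volume. This makes a large shift less likely, but nothing fixes the shares and the delayed Kenyan start works against balance.
- **The mix problem may not arise.** As far as the v5.0 updated timeline can be read, Kenya shows only late baseline collection and no intervention period. A Jinja-versus-Gulu analysis has one hospital per group and no mix to shift. This stands, but neither document specifies that analysis. Equally, neither plans to pool Kenyan baseline data without a Kenyan Phase III, so the large shift this would cause should not be presumed.
- **Partly covered already.** The country subgroup would give estimates free of mix shift and could expose an artefact, and the confounder clause mentions changes in patient populations. Neither changes the primary estimate.
- **Gulu.** A reader might infer that the published model breaks down because Gulu changes role, or that Kenyan and Gulu data cannot be combined. The documents do not support this. The group dummy belongs to a three-site plan in which every role is fixed. Gulu appears only in v5.0, whose analysis section has no such dummy, and its role during Jinja's Phase III is stated. Nobody proposes coding its later data as control. What remains is that the two plans need reconciling and that the use of Gulu's later data is unstated.

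**Conclusion.** The primary model as published leaves the effect open to bias from a change in site mix, equal to the baseline-rate gap times the shift in share. Under assumed gaps of 10 and 15 points with shifts of 20 and 30 points, that is 2.0 and 4.5 points against a planned 5.4. The documents support neither a firm size nor a direction. The bias is zero if the rates are equal, the mix is constant, or a single intervention hospital is analysed.

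This is a should-fix: the exposure is avoidable at almost no cost. The Gulu issue is a separate matter of reconciling two documents, not a defect of the published model on its own terms.

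**What to change.** 1. In the primary model, replace the group main effect with site fixed effects. Keep phase, and keep the phase-by-intervention term, defined as the tool being in use at this site.
2. Report marginal risk differences standardised to a fixed, pre-stated site mix. Keep the country-specific estimates as planned.
3. State which analysis governs, the published difference-in-differences model or section 17 of v5.0, and list the coding of each hospital in each period. Code Gulu as control during Jinja's Phase III. Do not count its post-switch data as control: either exclude them from the primary contrast or code them as treated.
4. Calendar-period terms can be offered as sensitivity analyses. With so few hospitals and one control at a time they rest on little information, so they need not be in the primary model.

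**Cost.** In the three-site design the model goes from four parameters (intercept, phase, group, interaction) to five (intercept, two site terms, phase, tool in use). No new data are needed, because each child's hospital and enrolment date are already recorded.

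**Limits.** Site effects remove the composition bias. They do not remove different time trends between hospitals, and with two to four hospitals the between-site uncertainty remains understated. Both should be acknowledged in the plan.
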